Patients/caregivers will be instructed to fill in the electronic diary (eDiary) every morning and evening for the first 24 weeks (Visit 1 through Visit 5) and the 21 days before each clinic visit thereafter (Visit 6 through Visit 12). In addition, Cohort 2 patients/caregivers will be instructed to fill in the eDiary during the screening period. Patients participating in the optional extension period will stop eDiary entries at Visit 11. The eDiary will include patient reported outcome (PRO) and observer-reported outcome (ObsRO) items for evaluation of itching (PRO), scratching (ObsRO), and sleep disturbance (PRO and ObsRO). Observer-reported outcomes in patients of all ages will be recorded by a caregiver. If possible, the same caregiver will complete the ObsRO items throughout the study. Additionally, caregivers will be requested to report in the diary the time that study drug was administered during the Treatment Period.

The patient will return to the clinic after 4 weeks and 12 weeks and thereafter every 10 to 12 weeks for follow-up measurements. Between the clinic visits there will be a telephone contact with the patient/caregiver to report AEs.

At Visit 11, patients will be offered the choice to continue receiving A4250 treatment in an optional extension period. In the extension period the patient will continue to receive A4250 at the same dose as at the end of the 72-week treatment period, returning to clinic every 16 weeks until the drug is commercially available, provided continued use is supported by the risk-benefit profile and the subject has not been previously withdrawn or discontinued from study.

If the patient is prematurely withdrawn from the study, all assessments scheduled for Visit 11 will be performed at the time the patient withdraws. If a patient participating in the optional extension study withdraws prior to commercial drug availability, all assessments scheduled for the optional Extension Period End of Treatment visit will be performed.

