7.2.3 Withdrawal of Patients

Patients/caregivers will be informed that they have the right to withdraw from the study at any time, without prejudice to their medical care, and that they are not obliged to state their reasons.

Any withdrawal, and reasons for withdrawal, must be fully documented in the eCRF and source documents and the patient followed by the investigator/investigative staff. Withdrawn patients will not be replaced.

Patients will be withdrawn in the following circumstances:

- A patient's/caregiver's desire for withdrawal for any reason
- Lost to follow-up (every effort must be made to contact the patient/caregiver; a certified letter must be sent)
- An AE which, in the opinion of the investigator, necessitates withdrawal
- Death
- A patient's/caregiver's substantial non-compliance (eDiary and study drug compliance) or protocol violation
- An investigator's opinion that continuing the patient in the study is not appropriate. The investigator may withdraw a patient at any time, if it is considered to be in the patient's best interest
- Liver transplantation

The reason and the date the patient is withdrawn from the study will be documented in the eCRF and source documents. If a patient is withdrawn from further treatment with the study drug, the investigator/investigative staff will attempt to complete all Visit 11 procedures at the time the patient is prematurely withdrawn from the study. The investigator/investigative staff will also attempt to complete all Visit 12 procedures 28 days following premature withdrawal (i.e., 28 days following the final dose of the study drug).

If a patient discontinues prior to Week 72, additional telephone contacts will be made every 3 months after the Follow-up Visit (Visit 12) up to Week 72 to gather whether or not the patient has had biliary diversion or liver transplantation, and of ongoing TEAEs at the time of discontinuation have resolved. The telephone calls will take place up until 72 weeks even if the patient has biliary diversion or liver transplant.

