9 ASSESSMENT OF EFFICACY

9.1 Efficacy Endpoints

9.1.1 Primary Efficacy Endpoints

The primary efficacy endpoints are:

EU and rest of world: Change from baseline in serum bile acids after 72 weeks of treatment.

US: Proportion of positive pruritus assessments at the patient level over the 72-week treatment period using the Albireo ObsRO instrument.

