11.2.2.2 Missing Data

Missing data will be reported descriptively. In general, imputations of missing observations will not be made. Any additional sensitivity analysis concerning missingness and details regarding handling of missing data will be described in the statistical analysis plan (SAP).

Continued collection of efficacy data for patients who discontinue treatment will be made as far as possible.

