11.2.2.5 Evaluation of Primary Efficacy Variables

The proportion of positive pruritus assessments at the patient level over the 72-week treatment period will be summarized. A positive pruritus assessment is defined as a scratching score of ≤ 1 or at least a one-point drop from baseline on the Albireo ObsRO instrument. At each assessment, the AM score will be compared to the baseline AM average, and the PM score will be compared to the baseline PM average. Both AM and PM pruritus assessments will be included in the analysis of this endpoint. Baseline will be defined as the average score from 14 days prior to treatment start in Study A4250-008 for AM and PM, respectively.

Fasting serum bile acids baseline will be calculated as the average of the pre-dose value in Study A4250-008 (Visit 1) and the previous visit (Visit 8 in study A4250-005) for Cohort 1. Fasting serum bile acids baseline will be calculated as the average of Visit S-2 and the pre-dose Visit 1 values in Study A4250-008 for Cohort 2. The end value is the average of the values at Weeks 70 and 72 in study A4250-008.

The change from baseline over the Treatment Period in serum bile acids will be analyzed mainly by using descriptive statistics. Change over time will also be displayed using graphical presentations (e.g., a spaghetti plot which illustrates the change in both Study A4250-005 and Study A4250-008 by treatment group in Study A4250-005). In addition, change from baseline 1 to end of treatment will be analyzed by using one-sample T-test or Wilcoxon signed-rank test as appropriate.

As an exploratory analysis of pruritus and serum bile acids, a comparison of treatment with A4250 120 $\mu\text{g}/\text{kg}/\text{day}$ during the first 24 weeks of Study 008 vs placebo patients over the 24-week treatment period from Study 005 will be carried out.

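### The bile acid end value needs Weeks 70 and 72, so the FAS summary is in practice completers only; the Baseline 1 test uses an undefined end of treatment, and samples after surgery have no rule

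*Protocol*

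**What the plan says.** Section 9.1.1 makes serum bile acids primary outside the US: "EU and rest of world: Change from baseline in serum bile acids after 72 weeks of treatment". Section 11.2.2.5 fixes the end value: "The end value is the average of the values at Weeks 70 and 72 in study A4250-008". The primary baseline is a two-sample average (Visit 8 of A4250-005 with Visit 1 for Cohort 1; Visit S-2 with Visit 1 for Cohort 2).

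The same section adds a test: "change from baseline 1 to end of treatment will be analyzed by using one-sample T-test or Wilcoxon signed-rank test as appropriate". Section 11.2.2.1 defines Baseline 1 for Cohort 1 only. Section 11.2.2.5 does not define end of treatment. Table 1 attaches that label to Visit 11, and section 7.1.3.3 heads the same visit as end of treatment and early termination together.

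On missing data, section 11.2.2.2 says "In general, imputations of missing observations will not be made", leaves the details to the SAP, and adds "Continued collection of efficacy data for patients who discontinue treatment will be made as far as possible". Section 11.2.1 makes the FAS (at least one dose) the primary set.

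On leaving early, section 7.1.1 says "If the patient is prematurely withdrawn from the study, all assessments scheduled for Visit 11 will be performed at the time the patient withdraws", and section 7.2.3 says "If a patient is withdrawn from further treatment with the study drug, the investigator/investigative staff will attempt to complete all Visit 11 procedures". Visit 12 follows 28 days after the last dose and includes a bile acid sample (section 7.1.3.4). After that there are only three-monthly calls to Week 72, about diversion, transplantation and ongoing TEAEs. Section 7.2.3 lists liver transplantation and death among the withdrawal reasons. It does not list biliary diversion, which sections 5.2.1 and 5.3 describe as a way to lower systemic bile acids.

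**The concern.** The end-value rule and the visit schedule do not fit an analysis on all treated patients. Someone who withdraws at Week 30, say, has an exit sample and a Visit 12 sample but is not scheduled for Week 70 or 72, so has no end value. The summary is labelled FAS but describes those who stayed. In a single-arm study no comparator loses patients in the same way, so if patients leave because the drug is not working, the reported reduction is too favourable.

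Two further gaps sit in the same section. First, a programmer could read end of treatment as the Week 70/72 mean (completers) or as the Visit 11/EOT sample at any week (completers and leavers). The test could then rest on different patients and times from the summary beside it. Second, nothing says what to do with a sample drawn after surgery. A patient diverted during the study who stays in it can have Week 70/72 values lowered by the operation, and these would count as drug effect in the primary summary itself.

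**Working it through.** **The plan's own figure.** The only power statement (section 11.1) concerns diversion, transplantation or death: 89% to 96% for an upper confidence limit below 30% when the true proportion is 10%, n = 48 to 60. An exact binomial calculation with the Clopper-Pearson limit reproduces it. At n = 48, at most 7 events are allowed (limit 27.8%), power 89.8%. At n = 60, at most 10 events (limit 28.5%), power 96.6%. This says nothing about bile acids. It only supplies 10% and 30% as event proportions that the plan itself contemplates.

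**Which samples exist**

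| Patient | Scheduled bile acid samples | Week 70/72 end value | Value if end of treatment means Visit 11 |
|---|---|---|---|
| Completes 72 weeks | Weeks 70 and 72 | yes | Week 72 |
| Withdraws early, no surgery | Visit 11 at exit, Visit 12 | none | exit sample |
| Withdrawn for transplantation | Visit 11 attempted at withdrawal, Visit 12 | none | exit sample, before or after surgery not fixed |
| Diverted on study, stays in | all visits | yes, after surgery | Week 72, after surgery |

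**Size of the completer effect.** All inputs are assumptions, because the protocol gives none: n = 60; half respond by −150 µmol/L and half by 0; within-group SD of change 80; 20% of non-responders leave and no responders do.

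- Leavers as a share of all: 0.5 × 0.20 = 10%.
- All-patient mean: 0.5 × (−150) + 0.5 × 0 = −75.
- Completers: 30 responders and 24 non-responders; mean = 30 × (−150) / 54 = −83.3.
- Difference: 8.3 µmol/L, or 8.3/75 = 11%.
- Standard error of the mean change: √(80² + 75²) / √60 = 109.7 / 7.75 = 14.2, so the difference is about 0.6 SE.

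A simulation that also assumes a baseline of 250 (SD 100) and floors values at zero gives about −67 and −74. The gap is similar.

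More generally, if leavers make up a share w and their change is zero, the completer mean equals the all-patient mean divided by (1 − w). For completers at −50% of baseline, the all-patient mean is 0.9 × (−50%) = −45% at w = 10% and 0.7 × (−50%) = −35% at w = 30%.

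**Worst case for the Baseline 1 test only.** Suppose end of treatment means the exit sample, every leaver is a transplant patient sampled after surgery, and the value is then about 10 µmol/L. The mean becomes 0.5 × (−150) + 0.4 × 0 + 0.1 × (10 − 250) = −75 − 24 = −99. None of these three conditions is stated in the protocol.

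**The case against.** The strongest reply is that section 11.2.2.2 leaves missing-data details to the SAP, which is not at hand, and that the study is mainly descriptive with no formal hypothesis testing. That stands against any complaint that detail is absent. It does not answer the point that the protocol itself fixes an end value which early leavers are not scheduled to have, and uses a second, undefined term beside it.

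A reader might infer more than the text supports:

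- **That withdrawn patients cannot have an end value.** They are not scheduled to have one. Someone who leaves between Weeks 70 and 72 could have both samples, and the protocol intends continued collection where possible.
- **That the continued-collection sentence has nothing behind it.** Visit 12 draws bile acids, and the later calls collect diversion and transplantation, which are efficacy outcomes. The sentence can stay.
- **That transplant patients score as best responders on the primary endpoint.** An exit sample does not enter a Week 70/72 mean. It could enter only the Baseline 1 test in Cohort 1, and only if end of treatment does not mean the end value defined shortly before it. Whether the sample follows surgery is not stated, nor is any post-transplant bile acid level.
- **That failures disappear from the report.** Change at each visit is a secondary endpoint (section 9.1.2), discontinuations are tabulated with reasons, and diversion, transplantation or death has its own interval and Kaplan-Meier analysis.

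The illustration also assumes an untreated baseline. Cohort 1 patients who took A4250 in A4250-005 have an on-drug primary baseline, so no change for them means a sustained effect. For that reason scoring failures as no change would be a poor remedy.

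**Conclusion.** The point holds in a limited form. As written, the primary bile acid summary outside the US is in practice restricted to completers although labelled FAS. The Baseline 1 test has an ambiguous endpoint that may bring in different patients and times. No rule covers samples after surgery, and diversion is the route by which a surgical effect could enter the primary summary.

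Under the stated assumptions the completer restriction moves the mean from −75 to about −83 µmol/L, roughly 0.6 standard errors. The direction rests on failures leaving preferentially, which is plausible but not documented, and the size rests on invented inputs. The −99 figure is a worst case for the Baseline 1 test and does not describe the primary endpoint. This should be corrected, but it does not invalidate the study.

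**What to change.** In section 11.2.2.5, carried into the SAP:

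1. State that end of treatment in the Baseline 1 test is the Week 70/72 end value, or define it explicitly otherwise.
2. Exclude from the efficacy change any bile acid sample drawn after a liver transplantation or biliary diversion performed during the period over which change is measured. The rule must be limited in this way because up to 40 Cohort 2 patients may enter after an earlier diversion, and their samples should stay in.
3. Beside the Week 70/72 result, report an FAS analysis that uses the last on-drug, pre-surgery sample for patients without a Week 70/72 value, including Visit 11 at exit where it qualifies. Flag these values as early termination, not Week 72, and give the number of leavers by reason.

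Do not assign a no-change score to transplantation or death, and keep the continued-collection sentence.

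Cost: wording and one additional analysis from samples already scheduled. The reported reduction may become slightly less favourable.

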11.2.2.6 Evaluation of Secondary and Exploratory Efficacy Variables

All secondary and exploratory variables listed under [Sections 9.1.2](#) and [9.1.3](#) will be analyzed descriptively for categorical and continuous data, as applicable. For continuous data, the change from baseline will be analyzed in addition to the actual visit values. For categorical data, shift tables or frequency and percentages of patients will be presented as appropriate.

Change in growth (Z-score, SD from P50 standard growth curve) will be analyzed by using one-sample T-test or Wilcoxon signed-rank test as appropriate. Change in growth (height/length for age, weight for age, BMI, and mid-arm circumference) will also be displayed using graphical presentations.

A 95% CI will be calculated for the proportion of patients experiencing surgical bile diversion or liver transplantation or death as well as for the proportion of patients experiencing surgical bile diversion or death or liver transplantation. The upper boundary will be compared to the

expected proportion of events, using the event probability estimated from the untreated reference population in an ongoing observational cohort study.

Time to first event, i.e., time to surgical bile diversion or liver transplantation or death, will be explored by descriptive statistics and Kaplan-Meier curves, which also will be used to make a comparison to the NAPPED population. The propensity score matched cohort analysis using inverse probability of treatment weights will be used to match the study patient population to the reference population based on age group and PFIC type.

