7 INVESTIGATIONAL PLAN

7.1 Overall Study Design and Plan

7.1.1 Description

This is a Phase 3, multi-center, open-label extension study to investigate the long-term efficacy and safety of a 120 µg/kg daily dose of A4250 in patients with PFIC, including episodic forms also referred to as BRIC. Cohort 1 will consist of children with PFIC Types 1 and 2 who have participated in Study A4250-005. Cohort 2 will consist of approximately 60 patients with any type of PFIC who have elevated serum bile acids and cholestatic pruritus and who either (1) do not meet eligibility criteria for Study A4250-005 (PEDFIC 1) or (2) are eligible for enrolment in A4250-005 after recruitment of study A4250-005 has been completed. Up to 40 patients post biliary diversion surgery are allowed to participate in Cohort 2.

The study includes a 72-week Treatment Period and a 4-week Follow-up Period. Patients who wish to continue receiving A4250 after 72 weeks will have the option to remain on treatment in an extension period with visits every 16 weeks until the drug is commercially available, provided continued use is supported by the risk-benefit profile and the subject has not been previously withdrawn or discontinued from the study. In that case the 4-week Follow-up Period will not occur.

The study data will be reviewed periodically (approximately on a quarterly basis) by a Data Safety and Monitoring Board (DSMB) until the last patient reaches 72 weeks.

Eligible patients will be enrolled into this open-label extension study and treated with a daily dose of 40 µg/kg/day³ or 120 µg/kg/day of A4250 for 72 weeks, or 40 µg/kg/day for the first 12 weeks followed by 120 µg/kg/day for the remaining 60 weeks³. Patients not tolerating the 120 µg/kg/day dose after a minimum of 1 week for reasons other than new liver findings and severe diarrhea, as described in [Section 10.2.2](#), will have the option to down-titrate to a lower dose (40 µg/kg/day). The patient should return to the higher dose as soon as deemed appropriate by the investigator. More than one upward dose titration (from 40 µg/kg/day directly to 120 µg/kg/day) for the same event is not recommended. Any dose titration should be done in consultation with the sponsor Medical Monitor or designee.

Patients participating in the optional extension period will continue on a daily dose of 40 µg/kg/day or 120 µg/kg/day of A4250 with the option to down-titrate to a lower dose (40 µg/kg/day).

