7.2.2 Exclusion Criteria

Patients meeting any of the following criteria at Visit 1 or Visit S-1 will not be eligible for study participation:

Cohort 1:

1. Decompensated liver disease: coagulopathy, history, or presence of clinically significant ascites, variceal hemorrhage, and/or encephalopathy.
2. Sexually active males and females who are not using a reliable contraceptive method with $\leq 1\%$ failure rate (such as hormonal contraception, intra-uterine device, or complete abstinence) throughout the duration of the study and 90 days thereafter (from signed informed consent through 90 days after last dose of study drug). See [Appendix 6](#) for further details.
3. Patients not compliant with treatment in study A4250-005.
4. Any other conditions or abnormalities which, in the opinion of the investigator or Medical Monitor, may compromise the safety of the patient, or interfere with the patient participating in or completing the study.

Cohort 2:

1. Known pathologic variations of the ABCB11 gene that have been demonstrated to result in complete absence of the BSEP protein.

2. Patient with past medical history or ongoing presence of other types of liver disease including, but not limited to, the following:
 - a) Biliary atresia of any kind.
 - b) Suspected or proven liver cancer or metastasis to the liver on imaging studies.
 - c) Histopathology on liver biopsy is suggestive of alternate non-PFIC related etiology of cholestasis.
- Note: Patients with clinically significant portal hypertension are allowed.
3. Patient with a past medical history or ongoing presence of any other disease or condition known to interfere with the absorption, distribution, metabolism (specifically bile acid metabolism), or excretion of drugs in the intestine, including but not limited to, inflammatory bowel disease.
4. Patient with past medical history or ongoing chronic (i.e., >3 months) diarrhea requiring intravenous fluid or nutritional intervention for treatment of the diarrhea and/or its sequelae.
5. Patient has a confirmed past diagnosis of infection with human immunodeficiency virus or other present and active, clinically significant, acute, or chronic infection, or past medical history of any major episode of infection requiring hospitalization or treatment with parenteral anti-infective treatment within 4 weeks of treatment start (Study Day 1) or completion of oral anti-infective treatment within 2 weeks prior to start of Screening Period.

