6. Any patient with suspected or confirmed cancers except for basal cell carcinoma, and non-liver cancers treated at least 5 years prior to Screening with no evidence of recurrence.
7. Patient has had a liver transplant, or a liver transplant is planned within 6 months of the Screening/Inclusion Visit.
8. Decompensated liver disease, coagulopathy, history, or presence of clinically significant ascites, variceal hemorrhage, and/or encephalopathy.
9. INR >1.4 (the patient may be treated with Vitamin K intravenously, and if INR is \leq 1.4 at resampling the patient may be included).
10. Serum ALT $>10 \times$ upper limit of normal (ULN) at Screening.
11. Serum ALT $>15 \times$ ULN at any time point during the last 6 months unless an alternate etiology was confirmed for the elevation.
12. Total bilirubin $>10 \times$ ULN at Screening.
13. Patient suffers from uncontrolled, recalcitrant pruritic condition other than PFIC. Examples include, but not limited to, refractory atopic dermatitis or other primary pruritic skin diseases.

14. Any patient who is pregnant or lactating or who is planning to become pregnant within 72 weeks of the Screening/Inclusion Visit.
15. Sexually active males and females who are not using a reliable contraceptive method with $\leq 1\%$ failure rate (such as hormonal contraception, intrauterine device, or complete abstinence) throughout the duration of the study and 90 days thereafter (from signed informed consent through 90 days after last dose of study drug). See [Appendix 6](#) for further details.
16. Patient with a past medical history of alcohol or substance abuse will be excluded. Patient must agree to refrain from illicit drug and alcohol use during the study.
17. Administration of bile acid or lipid binding resins and medications that slow GI motility (Refer to [Appendix 1](#) – Concomitant Medications Guidelines).
18. Patient has had investigational exposure to a drug, biologic agent, or medical device within 30 days prior to Screening, or 5 half-lives of the study agent, whichever is longer.
19. Any other conditions or abnormalities which, in the opinion of the investigator or Medical Monitor, may compromise the safety of the patient, or interfere with the patient participating in or completing the study.

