11 STATISTICAL EVALUATION

11.1 Sample Size and Power

There is no formal hypothesis testing in this open label study. Sample size for Cohort 1 was determined in Study A4250-005. For Cohort 1, patients will be enrolled following completion or participation of 12 weeks of Study A4250-005. The expected proportion of patients with at least one event, i.e., surgical bile diversion or liver transplantation or death, in untreated patients is expected to be high enough to be able to detect an improvement after A4250 treatment. For the other endpoints, mainly descriptive analyses will be performed.

The proportion of patients with at least one event (i.e., surgical bile diversion or liver transplantation or death), that can be expected in a non-treated population depends on PFIC type and age distribution of the included patients. The expected proportion of patients with events will be calculated for the study population once each patient's age and PFIC type are known, using the probability that a patient will get an event estimated from the reference population in the ongoing observational cohort study, NAtural Course and Prognosis of PFIC and Effect of Biliary Diversion (NAPPED).

As an example, if the expected proportion with at least one event is estimated to be 30% in the study population, and then if the proportion of patients with at least one event during A4250 long-term treatment are shown to be only 10% in the study, the power is approximately 89% to 96% (1-sided test, alpha=2.5%) for a confidence interval (CI) with upper boundary <30% based on a sample size of n=48 to 60. The sample size of 60 patients for Cohort 2 was estimated based on the availability of target patient population to evaluate the therapeutic benefit for those patients.

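### The NAPPED benchmark for diversion, transplant or death is set by age and PFIC type only, so it does not describe a population with up to 40 already-diverted patients and with high-risk patients excluded

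*Protocol*

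**What the plan says.** Protocol section 11.1 defines the event as surgical bile diversion, liver transplantation or death and takes its untreated rate from NAPPED: "The expected proportion of patients with events will be calculated for the study population once each patient's age and PFIC type are known". Section 11.2.2.6 compares the upper limit of a 95% CI for the observed proportion with that expected proportion. It adds a Kaplan-Meier comparison with NAPPED in which a propensity-score procedure "will be used to match the study patient population to the reference population based on age group and PFIC type". Both sections speak of the study population as a whole. The synopsis ties the same 30% example to Cohort 1.

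On who is enrolled, section 7.1.1 states: "Up to 40 patients post biliary diversion surgery are allowed to participate in Cohort 2". Section 7.2.2 excludes from Cohort 2 the following: "Patient has had a liver transplant, or a liver transplant is planned within 6 months of the Screening/Inclusion Visit"; decompensated liver disease; INR above 1.4 (unless corrected on resampling); total bilirubin above 10 times ULN; and "Known pathologic variations of the ABCB11 gene that have been demonstrated to result in complete absence of the BSEP protein". For Cohort 1 it excludes decompensated disease. Section 7.2.1 also requires Cohort 1 patients to have completed 24 weeks of Study A4250-005, or at least 12 weeks if they withdrew for intolerable symptoms.

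No section limits the event comparison to undiverted patients or applies the trial's criteria to NAPPED.

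**The concern.** The event includes a first diversion. A patient diverted before entry has largely used up that component, yet age and PFIC type alone give that patient the expected risk of an undiverted one. The exclusions act within age group and PFIC type: absence of BSEP is a subset of Type 2, and decompensation or a planned transplant can occur in any type. Weighting on age and type cannot remove such patients from the reference.

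Reducing diversion and transplantation is a secondary objective (section 6.2) and part of the rationale for the drug (section 5.3). If the benchmark belongs to a different population, a favourable result cannot be attributed to A4250. The protocol text itself names the two variables, so this is not a detail left open for the SAP.

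Section 11.2.2.6 also has two drafting faults. It names a matched cohort and inverse probability weights as if they were one method. It also announces a second CI, "as well as for the proportion of patients experiencing surgical bile diversion or death or liver transplantation", which is the first composite in a different order.

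**Working it through.** **Inputs from the protocol.** Benchmark 30%, rate on A4250 10%, n = 48 to 60, one-sided alpha 2.5%, stated power about 89% to 96% (section 11.1). Up to 40 diverted patients in a Cohort 2 of about 60, and about 120 patients in both cohorts (section 7.1.1, synopsis). The documents give no NAPPED rates, so the event risks below are assumptions.

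**Step 1: reproduce the stated power.** The exact (Clopper-Pearson) upper bound for x events in n is U = Beta⁻¹(0.975; x+1, n−x). The criterion is U < 0.30.
- n=48: met if x ≤ 7. P(X ≤ 7 | 10%) = 89.8%.
- n=60: met if x ≤ 10. P(X ≤ 10 | 10%) = 96.6%.
- n=120: met if x ≤ 25.

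The stated figures reproduce. The power statement is not wrong; it assumes that the benchmark applies to the patients enrolled.

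**Step 2: no drug effect, fair benchmark.** With a true rate of 30%, the criterion is met with probability 1.1% (n=48), 1.4% (n=60) and 1.6% (n=120).

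**Step 3: no drug effect, diverted patients at lower risk.** Assume 40 diverted patients at risk r and the rest at 30%. The event count is the sum of Bin(40, r) and Bin(n−40, 0.30). The mean rate is [40r + (n−40)(0.30)]/n.

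| r (assumed) | Mean rate, n=60 | P(U<30%), n=60 | Mean rate, n=120 | P(U<30%), n=120 |
|---|---|---|---|---|
| 20% | 23.3% | 14.0% | 26.7% | 8.6% |
| 15% | 20.0% | 32.0% | 25.0% | 16.8% |
| 10% | 16.7% | 58.4% | 23.3% | 29.4% |

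The n=60 columns are Cohort 2 alone, and the n=120 columns are both cohorts. With 20 diverted patients at 15%, the probability is 8.3% (n=60) or 5.8% (n=120).

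**Step 4: planned-transplant exclusion alone.** Assume that transplants are half of the 30%, fall evenly over 72 weeks, and that all those in the first 26 weeks were planned at screening. The excluded share is 15% × 26/72 = 5.4%. These patients leave both numerator and denominator: (30 − 5.4)/(100 − 5.4) = 24.6/94.6 = 26.0%. At n=60 the criterion is then met with probability 6.2%.

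**Step 5: benchmark treated as known.** Suppose the benchmark is itself estimated from N reference patients with a true rate of 30%, and the trial's true rate is also 30%. At n=60 the one-sided error is 7.2%, 4.4% or 3.1% for N = 50, 100 or 200 (assumed sizes).

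**Step 6: the opposite direction.** If the enrolled patients' untreated risk were 35%, the probability at n=60 would fall to 0.1%, and a real effect would be harder to show.

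**The case against.** Several points on the other side are sound.

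- **Direction.** A reader might infer that the bias must favour A4250. The documents do not establish this. Cohort 2 patients without BRIC need bile acids of at least 100 µmol/L and a scratching or itch score of at least 2 (section 7.2.1), and section 5.2.1 names resistant pruritus as the leading indication for diversion. Diverted patients who still meet these thresholds may have failed diversion, which section 5.2.1 links to transplantation. Portal hypertension is allowed. The 10% to 20% assumed for diverted patients has no source in the protocol.
- **Status.** A reader might say that a 2.5% type I error is being breached. Section 11.1 disclaims formal testing and offers the power figure as an example. The endpoint is secondary, and both primary endpoints are unaffected.
- **Only control.** A reader might take this as the trial's only comparison with patients not on the drug. It is not: section 11.2.2.5 plans an exploratory 24-week comparison with A4250-005 placebo patients for pruritus and bile acids. It is the only such comparison for these events.
- **Cohort.** The diverted patients and most of the exclusions belong to Cohort 2, while the synopsis ties the example to Cohort 1. The 32% figure is therefore not a figure for the whole study.
- **Unseen material.** The make-up of the untreated NAPPED reference is not shown, and an SAP could filter it.

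What remains is that sections 11.1 and 11.2.2.6 name two variables, apply them to the whole study population and make no provision for prior diversion. An SAP that follows them inherits the mismatch.

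**Conclusion.** The point holds as a mismatch between benchmark and population that can produce an apparent benefit without a drug effect. It does not show that such a benefit will appear. On the assumptions in step 3, with the cap of 40 fully used, the criterion is met by an inactive drug with probability 14% to 58% in Cohort 2 alone and 9% to 29% in both cohorts, against about 1.5% with a fair benchmark. These figures scale with the number of diverted patients actually enrolled and with their true risk, and they would reverse if that risk exceeded the benchmark. For Cohort 1 alone, the concern reduces to the decompensation exclusion and to selection through Study A4250-005, for which the documents allow no figure. The duplicated composite and the mixed naming of matching and weighting are plain drafting errors.

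**What to change.** 1. State which cohort is compared with NAPPED, reconciling the synopsis with sections 11.1 and 11.2.2.6.
2. Run the composite comparison only in patients without diversion at their first A4250 dose. Report previously diverted patients separately on transplant or death.
3. Apply the trial's exclusions to the NAPPED reference where the data are recorded, and start follow-up at an aligned time zero.
4. Weight the reference to the trial patients and drop the word for matching.
5. Report observed minus expected with an interval that carries NAPPED's sampling error, for example by bootstrap.
6. Correct the duplicated composite in section 11.2.2.6 by stating which second endpoint was meant.

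This needs changes of wording and a filter on the reference data, with no new trial procedures. The cost is fewer evaluable Cohort 2 and reference patients, and hence a wider interval.
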